11.1.3 Expectedness

Adverse events can be 'Expected' or 'Unexpected.'

11.1.4 Expected adverse event

Expected adverse events are those that have been previously identified as resulting from administration of the agent. For the purposes of this study, an adverse event is considered expected when it appears in the current adverse event list or is included in the informed consent document as a potential risk.

Refer to Section 6.1 for a listing of expected adverse events associated with the study agent(s).

11.1.5 Unexpected adverse event

For the purposes of this study, an adverse event is considered unexpected when it varies in nature, intensity or frequency from information provided in the current adverse event list or when it is not included in the informed consent document as a potential risk.

11.1.6 Attribution

Attribution is the relationship between an adverse event or serious adverse event and the study treatment. Attribution will be assigned as follows:

- Definite The AE is clearly related to the study treatment.
- Probable The AE is likely related to the study treatment.
- Possible The AE may be related to the study treatment.
- Unlikely The AE is doubtfully related to the study treatment.
- Unrelated The AE is clearly NOT related to the study treatment.

11.2 Procedures for AE and SAE Recording and Reporting

Participating investigators will assess the occurrence of AEs and SAEs at all participant evaluation time points during the study.

All AEs and SAEs whether reported by the participant, discovered during questioning, directly observed, or detected by physical examination, laboratory test or other means, will be recorded in the participant's medical record and on the appropriate study-specific case report forms.

The descriptions and grading scales found in the revised NCI Common Terminology Criteria for Adverse Events (CTCAE) version 4.03 will be utilized for AE reporting. All appropriate treatment areas should have access to a copy of the CTCAE version 4.03. A copy of the CTCAE version 4.03 can be downloaded from the CTEP website at:

http://ctep.cancer.gov/protocolDevelopment/electronic_applications/ctc.htm.

11.3 Adverse Events: List and Reporting Requirements

11.3.1 Expedited Adverse Event Reporting

Investigators **must** report to the Overall PI any serious adverse event (SAE) that occurs after the initial dose of study treatment, during treatment, or within 30 days of the last dose of treatment on the local institutional SAE form.

For multi-institution studies where a DF/HCC investigator is serving as the Overall Principal Investigator, each participating institution **must** abide by the reporting requirements set by the DF/HCC. This applies to any medical event equivalent to an unexpected grade 2 or 3 with a possible, probable or definite attribution, unexpected grade 4 toxicities, and grade 5 (death) regardless of study phase or attribution.

11.3.2 DF/HCC Expedited Reporting Guidelines

Investigative sites within DF/HCC and DF/PCC will report SAEs directly to the DFCI Office for Human Research Studies (OHRS) per the DFCI IRB reporting policy.

Other investigative sites will report SAEs to their respective IRB according to the local IRB's policies and procedures in reporting adverse events. A copy of the submitted institutional SAE form should be forwarded to the Overall PI within the timeframes detailed in the table below.

	DF/HCC Reportable AEs					
Attribution	Gr. 2 & 3 AE Expected	Gr. 2 & 3 AE Unexpected	Gr. 4 AE Expected	Gr. 4 AE Unexpected	Gr. 5 AE Expected or Unexpected	
Unrelated Unlikely	Not required	Not required	5 calendar days [#]	5 calendar days	24 business hours*	
Possible Probable Definite	Not required	5 calendar days	5 calendar days [#]	5 calendar days	24 business hours*	
# If listed in protocol as expected and not requiring expedited reporting, event does not need to be reported.						
* For participants enrolled and actively participating in the study or for AEs occurring within 30 days of the last intervention, the AE should be reported within 24 business hours of learning of the event.						

The Overall PI will submit SAE reports from outside institutions to the DFCI OHRS according to DFCI IRB policies and procedures in reporting adverse events.

11.4 Reporting to the Study Sponsor

11.4.1 Serious Adverse Event Reporting

All serious adverse events that occur after the initial dose of study treatment, during treatment, or within 30 days of the last dose of treatment must be reported to the DF/HCC Overall Principal Investigator on the local institutional SAE form. This includes events meeting the criteria outlined in Section 10.1.2, as well as the following:

- Grade 2 (moderate) and Grade 3 (severe) Events Only events that are unexpected and possibly, probably or definitely related/associated with the intervention.
- All Grade 4 (life-threatening or disabling) Events Unless expected AND specifically listed in the protocol as not requiring reporting.

• All Grade 5 (fatal) Events – When the participant is enrolled and actively participating in the trial OR when the event occurs within 30 days of the last study intervention.

Note: If the participant is in long term follow up, report the death at the time of continuing review.

Participating investigators must report each serious adverse event to the DF/HCC Overall Principal Investigator within 1 business day of learning of the occurrence. In the event that the participating investigator does not become aware of the serious adverse event immediately (e.g., participant sought treatment elsewhere), the participating investigator is to report the event within 24 hours after learning of it and document the time of his or her first awareness of the adverse event. In the case of a medical emergency which may require unblinding, contact the Overall Principal Investigator. Report serious adverse events by telephone, email or facsimile to:

Within the following 24-48 hours, the participating investigator must provide follow-up information on the serious adverse event. Follow-up information should describe whether the event has resolved or continues, if and how the event was treated, and whether the participant will continue or discontinue study participation.

11.4.2 Non-Serious Adverse Event Reporting

Non-serious adverse events will be reported to the DF/HCC Overall Principal Investigator on the toxicity Case Report Forms.

11.5 Reporting to the Institutional Review Board (IRB)

Investigative sites within DF/HCC will report all serious adverse events directly to the DFCI Office for Human Research Studies (OHRS).

Other investigative sites should report serious adverse events to their respective IRB according to the local IRB's policies and procedures in reporting adverse events. A copy of the submitted institutional SAE form should be forwarded to:

The DF/HCC Principal Investigator will submit SAE reports from outside institutions to the DFCI Office for Human Research Studies (OHRS) according to DFCI IRB policies and procedures in reporting adverse events.

11.6 Reporting to the Food and Drug Administration (FDA)

The DF/HCC Overall Principal Investigator, as holder of the IND, will be responsible for all communication with the FDA. The DF/HCC Overall Principal Investigator will report to the FDA, regardless of the site of occurrence, any adverse event that is serious, unexpected and reasonably related (i.e., possible, probable, definite) to the study treatment.

Unexpected fatal or life-threatening experiences associated with the use of the study treatment will be reported to FDA as soon as possible but in no event later than 7 calendar days after initial receipt of the information.

All other serious unexpected experiences associated with the use of the study treatment will be reported to FDA as soon as possible but in no event later than 15 calendar days after initial receipt of the information.

Events will be reported to the FDA by telephone ([name]) or by fax ([name]) using Form FDA 3500A (Mandatory Reporting Form for investigational agents) or FDA Form 3500 (Voluntary Reporting Form for commercial agents). Forms are available at http://www.fda.gov/medwatch/getforms.htm.

11.7 Reporting to National Heart Lung and Blood Institute

The DF/HCC Overall Principal Investigator will report unanticipated problems or unexpected serious adverse events (fatal, life threatening or serious) that may be related to the study protocol to the NHLBI Program Officer within 7 days. If the event or problem is unexpected, and possibly/probably/or definitely related to the study drug and suggests greater risk of harm to the study participant(s) than was previously known or recognized will be reported within 30 calendar days.

11.8 Reporting to Hospital Risk Management

Participating investigators will report to their local Risk Management office any subject safety reports or sentinel events that require reporting according to institutional policy.

11.9 Monitoring of Adverse Events and Period of Observation

All adverse events, both serious and non-serious, and deaths that are encountered from initiation of study intervention, throughout the study, and within 30 days of the last study intervention should be followed to their resolution, or until the participating

investigator assesses them as stable, or the participating investigator determines the event to be irreversible, or the participant is lost to follow-up. The presence and resolution of AEs and SAEs (with dates) should be documented on the appropriate case report form and recorded in the participant's medical record to facilitate source data verification.

For some SAEs, the study sponsor or designee may follow-up by telephone, fax, and/or monitoring visit to obtain additional case details deemed necessary to appropriately evaluate the SAE report (e.g., hospital discharge summary, consultant report, or autopsy report).

Participants should be instructed to report any serious post-study event(s) that might reasonably be related to participation in this study. Participating investigators should notify the DF/HCC Overall Principal Investigator and their respective IRB of any unanticipated death or adverse event occurring after a participant has discontinued or terminated study participation that may reasonably be related to the study.

12 DATA AND SAFETY MONITORING

12.1 Data Reporting

12.1.1 Method

The QACT will collect, manage, and monitor data for this study.

12.1.2 Data Submission

The schedule for completion and submission of case report forms (paper or electronic) to the QACT is as follows:

Form	Submission Timeline		
Eligibility Checklist	Complete prior to registration with QACT		
On Study Form	Within 14 days of registration		
Baseline Assessment Form	Within 14 days of registration		
Treatment Form	Within 10 days of the last day of the cycle		
Adverse Event Report Form	Within 10 days of the last day of the cycle		
Response Assessment Form	Within 10 days of the completion of the cycle required for response evaluation		

CONFIDENTIAL This document is confidential. Do not disclose or use except as authorized.

Off Treatment/Off Study Form	Within 14 days of completing treatment or being taken off study for any reason	
Follow up/Survival Form	Within 14 days of the protocol defined follow up visit date or call	

12.2 Safety Meetings

During the phase II portion of the study, the DF/HCC Data and Safety Monitoring Committee (DSMC) will review and monitor toxicity and accrual data from this study. The committee is composed of clinical specialists with experience in oncology and who have no direct relationship with the study. Information that raises any questions about participant safety will be addressed with the Overall PI and study team.

The DSMC will review each protocol up to four times a year or more often if required to review toxicity and accrual data. Information to be provided to the committee may include: up-to-date participant accrual; current dose level information; DLT information; all grade 2 or higher unexpected adverse events that have been reported; summary of all deaths occurring with 30 days of intervention for Phase I or II protocols; for gene therapy protocols, summary of all deaths while being treated and during active follow-up; any response information; audit results, and a summary provided by the study team. Other information (e.g. scans, laboratory values) will be provided upon request.

The DF/HCC Data and Safety Monitoring Board (DSMB) will review and monitor study progress, toxicity, safety and other data from this trial during the Phase III portion of the study. The board is chaired by a medical oncologist from outside of DF/HCC and has external and internal representation. Information that raises any questions about participant safety or protocol performance will be addressed with the Principal Investigator, statistician and study team members. Should any major concerns arise, the DSMB will offer recommendations regarding whether or not to suspend the trial.

The DSMB will meet twice a year to review accrual, toxicity, response and reporting information. A DSMB review will also be triggered if the number of toxicity events (possible or definite grade 3 or 4 toxicity or major hemorrhage) prompts an automatic enrollment hold within either cohort or prior the next dosing cohort. Information to be provided to the DSMB may include: participant accrual, treatment regimen information, adverse events and serious adverse events reported by category, summary of any deaths on study, audit results, and a summary provided by the study team. Other information (e.g. scans, laboratory values) will be provided upon request.

12.3 Monitoring

Involvement in this study as a participating investigator implies acceptance of potential audits or inspections, including source data verification, by representatives designated by the DF/HCC Overall Principal Investigator (or Protocol Chair) or DF/HCC. The
purpose of these audits or inspections is to examine study-related activities and documents to determine whether these activities were conducted and data were recorded, analyzed, and accurately reported in accordance with the protocol, institutional policy, and any applicable regulatory requirements.

All data will be monitored for timeliness of submission, completeness, and adherence to protocol requirements. Monitoring will begin at the time of participant registration and will continue during protocol performance and completion. Refer to section 5 of Data Safety and Monitoring Plan for additional information regarding monitoring plan.

13 REGULATORY CONSIDERATIONS

13.1 Protocol Review and Amendments

This protocol, the proposed informed consent and all forms of participant information related to the study (e.g., advertisements used to recruit participants) and any other necessary documents must be submitted, reviewed and approved by a properly constituted IRB governing each study location.

Any changes made to the protocol must be submitted as amendments and must be approved by the IRB prior to implementation. Any changes in study conduct must be reported to the IRB. The DF/HCC Overall Principal Investigator (or Protocol Chair) will disseminate protocol amendment information to all participating investigators.

All decisions of the IRB concerning the conduct of the study must be made in writing.

13.2 Informed Consent

All participants must be provided a consent form describing this study and providing sufficient information for participants to make an informed decision about their participation in this study. The formal consent of a participant, using the IRB approved consent form, must be obtained before the participant is involved in any study-related procedure. The consent form must be signed and dated by the participant or the participant's legally authorized representative, and by the person obtaining the consent. The participant must be given a copy of the signed and dated consent document. The original signed copy of the consent document must be retained in the medical record or research file.

13.3 Study Documentation

The investigator must prepare and maintain adequate and accurate case histories designed to record all observations and other data pertinent to the study for each

research participant. This information enables the study to be fully documented and the study data to be subsequently verified.

Original source documents supporting entries in the case report forms include but are not limited to hospital records, clinical charts, laboratory and pharmacy records, recorded data from automated instruments, microfiches, photographic negatives, microfilm or magnetic media, and/or x-rays.

13.4 Records Retention

All study-related documents must be retained for the maximum period required by applicable federal regulations and guidelines or institutional policies.

13.5 Multi-center Guidelines

This protocol will adhere to the policies and requirements of the Dana-Farber/Harvard Cancer Center. The specific responsibilities of the DF/HCC Overall Principal Investigator (or Protocol Chair), Coordinating Center, and Participating Institutions are presented in the Dana-Farber/Harvard Cancer Center Multi-Center Data and Safety Monitoring Plan (see Appendix A).

- The DF/HCC Overall Principal Investigator/Coordinating Center is responsible for distributing all IND Action Letters or Safety Reports to all participating institutions for submission to their individual IRBs for action as required.
- Mechanisms will be in place to ensure quality assurance, protocol compliance, and adverse event reporting at each site.
- Except in very unusual circumstances, each participating institution will order the agent(s) directly from the supplier. A participating site may order the agent(s) only after the initial IRB approval for the site has been forwarded to the Coordinating Center.

14 STATISTICAL CONSIDERATIONS

The aim of this combined phase II/phase III trial is to evaluate isoquercetin as an effective anticoagulant in cancer patients.

14.1 Study Design/Endpoints

- 14.1.1 The primary endpoint of the Phase II trial is to investigate whether isoquercetin significantly reduces d-dimer values in cancer patients. D-dimer is a readily available biomarker used clinically in the prediction and diagnosis of VTE. In cancer cohorts, the D-dimer has modest specificity for predicting symptomatic thrombosis.⁵⁸ However, D-dimer remains the most validated surrogate marker of thrombin generation in vivo and symptomatic VTE.
 - 14.1.1.1 **Study Design**: The trial is a sequential cohort study of isoquercetin 500 mg and 1000 mg daily.
 - 14.1.1.2 Randomization: Patients will not be randomized.
 - 14.1.1.3 Accrual: Anticipated accrual is 10 patients per month across all study sites.

14.1.1.4 Sample Size Justification: Plasma D-dimer levels typically decrease at least 20% following the initiation of anticoagulation.⁵⁹ The sample size is based on a paired t-test of D-dimer concentrations measured on day 1 and end of treatment, to be performed separately for each arm. In the recently completed MicroTEC study, the median baseline D-dimer concentration for all cancer patients enrolled was 815 ug/L.⁴⁷ Based on an estimated standard deviation of 0.3 for the ratio of the D-dimer levels at day 56 over the D-dimer levels at day 1, a total of 26 subjects are needed per arm for a 90% power to declare the reduction significant if the true concentration at end of treatment is reduced by 20% in each isoquercetin arm (one-sided alpha 0.05). Estimated death or dropout of 5% prior to 56 days, the sample size will be increased to a total of total 30 per arm (onesided alpha 0.05). With 30 eligible patients per dose level, there is greater than 60% power to detect an unacceptable attributable grade 3 or 4 rate of 15% at 56 days using a one-sided 10% level exact binomial test in each dose level. (see table below)

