major toxicities in the 30 patients in Cohort B, then we will only consider proceeding to the phase III portion of the study with isoquercetin 500 mg daily.

- 14.1.1.6 **Primary endpoint analysis:** D-dimer concentrations will be compared for each patient at day 0 and end of treatment by a paired-t test analysis. Analysis will be performed on an intention to treat basis for patients who undergo randomization and completed the baseline and end of treatment D-dimer assessments.
- 14.1.1.7 Determination of continuation with phase III trial and selection of dose. Following completion of the phase II study, decision will be made by principal investigators whether to proceed with enrollment into the phase III trial. The decision to continue will be principally guided by whether either isoquercetin arm reached the primary endpoint definition. If both isoquercetin arms meet the primary endpoint then selection of dose will be based on degree of reduction in D-dimer levels in each arm relative to baseline and toxicity profile with special attention to major hemorrhage episodes. If neither isoquercetin arm results in significant reduction in d-dimer values relative to baseline, then consideration to advance to phase III will be made based on overall VTE rate in the combined isoquercetin arms. D-dimer is a recognized biomarker of the prothrombotic state but is known to lack specificity in cancer cohorts⁵⁸. Because it is possible that isoquercetin is an effective antithrombotic without altering plasma D-dimer values especially considering potential antiplatelet activity, we will also analyze the cumulative incidence of VTE collectively for the isoquercetin treated patients. A true cumulative incidence VTE rate of less than 10% would be considered promising in the combined isoquercetin arms, whereas a true cumulative incidence rate of 25% would not be worthy of further study. Treatment is considered promising among the 60 patients treated with isoquercetin when nine or fewer VTE are observed. This design has at least a 92% chance of concluding the treatment is effective when the true cumulative incidence

rate is 10%, and less than a 5% chance of concluding the treatment is effective when the true cumulative incidence rate is 25% or more (Fisher exact test). If determination to proceed to phase III is based on promising VTE rates, then the higher dose level of isoquercetin will be utilized.

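### Phase II D-dimer size: the SD is for a ratio but the primary test compares concentrations, so the 90% power is not shown; on the ratio scale the stated inputs give 21 per arm, not 26

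*Combined protocol and SAP*

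**What the plan says.** Section 14.1.1.4 names the test that was sized: "The sample size is based on a paired t-test of D-dimer concentrations measured on day 1 and end of treatment", done separately in each arm. The variability behind it is an "estimated standard deviation of 0.3 for the ratio of the D-dimer levels at day 56 over the D-dimer levels at day 1". The target is 90% power "if the true concentration at end of treatment is reduced by 20% in each isoquercetin arm (one-sided alpha 0.05"), and the result is that "a total of 26 subjects are needed per arm for a 90% power to declare the reduction significant". This is raised to 30 per arm for 5% death or dropout. On baseline level, the section says only that in an earlier trial by the same group "the median baseline D-dimer concentration for all cancer patients enrolled was 815 ug/L"; no measure of spread is given.

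Section 14.1.1.6 gives the primary analysis: "D-dimer concentrations will be compared for each patient at day 0 and end of treatment by a paired-t test analysis". It mentions no log or ratio transformation. Sections 1.1 and 10.3, by contrast, describe the D-dimer outcome as a relative reduction or relative change.

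Under 14.1.1.7 the decision to continue to phase III is "principally guided by whether either isoquercetin arm reached the primary endpoint definition". If neither arm succeeds, "then consideration to advance to phase III will be made based on overall VTE rate in the combined isoquercetin arms". The rule that chooses between doses on degree of D-dimer reduction and toxicity is written for the case in which both arms meet the endpoint.

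**The concern.** Two things do not fit together.

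- **Scale.** A ratio SD is unitless. It does not fix the SD of the within-patient change in ug/L unless the baseline distribution is also known. In a concentration test, patients with high baselines contribute large differences and dominate the variance. The sized quantity is therefore not the tested quantity.
- **Arithmetic.** Taken at face value on the ratio scale, the stated inputs do not give 26.

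The scale gap is the part with consequences. If the concentration test has less than 90% power, a true 20% reduction could be missed in one arm, which alters how the dose is chosen, or in both, which moves the phase III decision to the VTE-rate fallback.

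**Working it through.** **Inputs (14.1.1.4).** Reduction 20%, so a mean ratio of 0.8 against 1 and a difference of 0.2; ratio SD 0.3; one-sided alpha 0.05; power 90%; stated n = 26; enrolled 30; dropout 5%, so 30 × 0.95 = 28.5, taken as 28 evaluable.

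**1. Trying to reproduce 26 on the ratio scale.** Standardised difference d = 0.2/0.3 = 0.667.

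Normal approximation: n = ((1.645 + 1.282) / 0.667)² = 19.3, so 20. The exact figures use the noncentral t with n − 1 degrees of freedom and noncentrality d√n:

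| n | one-sided 0.05 | one-sided 0.025 |
|---|---|---|
| 20 | 89.0% | 80.7% |
| 21 | **90.4%** | 82.8% |
| 25 | 94.4% | 89.2% |
| 26 | **95.2%** | **90.4%** |
| 28 | 96.3% | 92.5% |

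The stated inputs need 21. The figure 26 is not reproduced.

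**2. Routes that do give 26.**

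- Ratio scale, one-sided 0.025, 90% power: n = 26 (90.4%).
- Ratio scale, one-sided 0.05, 95% power: n = 26 (95.2%).
- Log scale with SD 0.3/0.8 = 0.375 and difference −ln(0.8) = 0.223, one-sided 0.05, 90% power: n = 26 (90.4%; n = 25 gives 89.3%).

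The third route keeps both the printed alpha and the printed power. The documents describe none of the three.

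**3. Power of the test as written.** The documents give no baseline spread, so it has to be assumed. Assume a log-normal baseline with median 815 ug/L, independent of a ratio with mean 0.8 and SD 0.3; 28 evaluable; one-sided 0.05. Simulated power of the paired t-test on concentrations:

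| Baseline log-SD | Log-normal ratio | Normal ratio |
|---|---|---|
| 0.3 | 91% | 95% |
| 0.5 | 88% | 92% |
| 0.8 | 82% | 85% |
| 1.0 | 76% | 78% |
| 1.5 | 59% | 57% |

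Power falls below 90% once the log-SD exceeds about 0.4 (log-normal ratio) to 0.6 (normal ratio). Without assuming a distribution for the baseline, the usual t-test calculation says that 28 evaluable reach 90% only if the mean difference is at least 0.57 of the SD of the differences. The plan does not state that SD.

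**4. What this does to the decision.** Assume a true 20% reduction in both arms and independent cohorts. At log-SD 1.0 (76-78% per arm):

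- Both arms missed: 0.24² to 0.22², about 5-6%, against 0.10² = 1% at the claimed 90%.
- At least one arm missed: 1 − 0.78² to 1 − 0.76², about 40-42%, against 1 − 0.90² = 19%.

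At log-SD 0.8 both arms are missed about 2-3% of the time.

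**5. The log-ratio test.** If the geometric mean ratio is 0.8 and the ratio SD is 0.3, the log-SD s solves 0.8·exp(s²/2)·√(exp(s²) − 1) = 0.3, so s = 0.343. The arithmetic mean ratio is then 0.849. With d = 0.223/0.343 = 0.651, 22 are needed for 90% at one-sided 0.05 (90.4%) and 27 at 0.025 (90.2%). With 26 evaluable, power is 94% and 89%.

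**6. Why the raw ratio is not the first choice.** In the setting of step 5, the raw-ratio test sees 1 − 0.849 = 0.151 rather than 0.2. At 28 evaluable its simulated power is about 80%, against about 96% for the log ratio. With equal within-patient noise at both visits, the current concentration test then has about 92%, 83-84% and 76-77% at baseline log-SD 0.5, 0.8 and 1.0. Switching to the raw ratio can therefore be worse than leaving the test alone.

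**The case against.** **Relative change is evidently what is meant.** Sections 1.1 and 10.3 say so, and 14.1.1.7 speaks of reduction relative to baseline. This stands as a guide to the remedy, but the analysis section is the operative text and it names concentrations.

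**The size is generous.** On the ratio scale 26 exceeds 21, and 30 are enrolled. This stands: the arithmetic discrepancy alone harms no decision.

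**The power loss is assumed.** Baseline spread, distributional shape and independence from the ratio are all absent from the documents, and with a small spread the concentration test also exceeds 90%. This stands. A reader might take the planned subgroup with D-dimer above 1500 mcg/L (section 1.3) as evidence of wide spread. It is a secondary subgroup that also requires elevated tissue factor bearing microparticles, and no prevalence is given, so it cannot carry that inference.

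**The decision is protected.** Either arm can succeed, D-dimer only principally guides the choice, and there is a fallback. This largely stands for go/no-go, but not for dose selection, where a miss in one arm matters.

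**Alpha or power need not be misstated.** A reader might infer from 21 versus 26 that one of them was misprinted. The log-scale route with SD 0.375 keeps both, so the documents do not support that inference.

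**Conclusion.** The 90% power claim is not supported for the primary test as written, because the SD supplied belongs to a different quantity. This rests on the text alone. On the ratio scale, the stated inputs give 21 per arm rather than 26. That is a failure to reproduce in the conservative direction, and its source cannot be identified.

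A reader might go further and call phase II underpowered. The documents do not show that. Under the assumptions in the working, per-arm power runs from about 91-95% at baseline log-SD 0.3 to 76-78% at 1.0, and no document figure says where in that range, or outside it, this population lies. The effect on go/no-go is modest under the same assumptions (both arms missed about 5-6% of the time at log-SD 1.0, against 1%). The effect on dose selection is larger (at least one arm missed about 40-42%, against 19%). The plan should be corrected, but it is not shown to fail.

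**What to change.** Before any outcome data are seen:

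1. In 14.1.1.6, make the primary test one on the relative scale of sections 1.1 and 10.3. The preferred form is a one-sample t-test, in each cohort, of the log of the end-of-treatment/day 1 D-dimer ratio against 0.
2. In 14.1.1.4, name the same test and compute power from inputs on that scale. For example: geometric mean ratio 0.8 and ratio SD 0.3, hence log-SD 0.343; 22 evaluable for 90% at one-sided 0.05; 26 evaluable give 94% (89% at one-sided 0.025).
3. If the raw ratio or the concentration difference is kept instead, state its SD and the matching power. For the raw ratio with arithmetic mean 0.8 and SD 0.3, 26 gives 95% at one-sided 0.05 if the ratio is near normal; if it is log-normal, 28 gives about 93%.
4. Show the calculation behind 26, with its scale, alpha and power.

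**Cost.** No extra patients or samples; 30 per arm stands. It is a substantive amendment, because the hypothesis moves from the mean concentration difference to the geometric mean ratio. These can disagree: if the arithmetic mean ratio is 1 with a log-normal SD of 0.3, the geometric mean is 1/√1.09 = 0.96, and the log test rejects about 18-19% of the time at 26-28 evaluable. The amendment should say that the geometric mean ratio is the intended target.
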